Appendix 6. ECOG Performance Status

Grade	ECOG Performance Status
0	Fully active, able to carry on all pre-disease performance without restriction.
1	Restricted in physically strenuous activity but ambulatory and able to carry out work of a light or sedentary nature, eg, light house work, office work.
2	Ambulatory and capable of all self-care but unable to carry out any work activities. Up and about more than 50% of waking hours.
3	Capable of only limited self-care, confined to bed or chair more than 50% of waking hours.
4	Completely disabled. Cannot carry on any self-care. Totally confined to bed or chair.
5	Dead

Source: Oken M et al. 1982.⁶³

Appendix 7. Recommendations for Management of Infusion Related Reactions Including Allergic/Hypersensitivity Reactions, Cytokine Release Syndrome or Anaphylaxis

Following the first infusion of some monoclonal antibody therapeutics, some patients experience fever, headache, nausea, vomiting or hypotension. These AEs are generally ascribed to lysis of cellular targets, cytokine release, or complement activation.

Type 1 hypersensitivity or allergic (eg, shortness of breath, urticaria, anaphylaxis, angioedema) reactions are theoretically possible in response to any injected protein. Immune complex mediated Type 3 hypersensitivity reactions are similar to the AEs of Type 1 reactions but are likely to be delayed from the time of infusion and may include symptoms such as rash, urticaria, polyarthritis, myalgias, polysynovitis, fever, and, if severe, glomerulonephritis.

All patients should be closely observed while receiving investigational product infusions. Monitoring for clinical signs of a systemic reaction should continue thereafter for clinical signs of allergic reactions/hypersensitivity.

Infusion reactions

If chills and fever ($>100.4^{\circ}\text{F}/38.0^{\circ}\text{C}$) or hypotension occur, the infusion should be interrupted. Patients should be treated symptomatically according to best medical and nursing practice and the infusion should be restarted at 50% of the original rate.

If infusion reactions, characterized by fever and chills, and less commonly hypotension, are experienced either by an individual patient or in other patients, pretreatment medication may be administered prior to subsequent doses to reduce the incidence and severity. The following pretreatment regimen is suggested, although a different regimen based on local standard of care is permitted:

- Patients should be pretreated with acetaminophen and diphenhydramine (or other antihistamine) approximately 0.5 to 2 hours before each PF-06801591 administration. Pretreatment medications will not be supplied by Pfizer. Suggested starting doses are 650 to 1000 mg acetaminophen and 50 mg diphenhydramine (or equivalent of other antihistamine) IV or oral. Two (2) additional doses of acetaminophen may be administered approximately every 4-6 hours after the initial pretreatment or as needed.

Hypersensitivity reactions:

In the case of a hypersensitivity reaction, the patient will be treated symptomatically, with supportive care and further monitoring until the end of the study. Study infusions may be stopped.

Guidelines for the management of hypersensitivity reactions are as follows:

1. NCI-CTCAE Grade 1 allergic reaction or cytokine release syndrome:
 - a. Monitor for worsening condition. If the reaction worsens, stop the infusion. Use premedication for subsequent infusions, as described above.
2. NCI-CTCAE Grade 2 allergic reaction or cytokine release syndrome:
 - a. Stop PF-06801591 infusion.
 - b. Administer bronchodilators, oxygen, acetaminophen, etc. as medically indicated.
 - c. Resume infusion at 50% of previous rate once reaction has decreased to \leq Grade 1 in severity. Monitor closely for any worsening. If the reaction recurs, stop infusion. Institute premedication for subsequent infusions as described above.
3. NCI-CTCAE Grade 3 or Grade 4 allergic reaction or cytokine release syndrome or anaphylaxis:
 - Grade 3 anaphylaxis (hypersensitivity reaction) consists of symptomatic bronchospasm requiring parenteral medications with or without urticaria, allergy-related edema/angioedema, or hypotension.
 - Grade 4 anaphylaxis (hypersensitivity reaction) is a life-threatening event requiring urgent intervention.
 - a. Stop the PF-06801591 infusion immediately and disconnect infusion tubing from the patient.
 - b. Administer epinephrine, bronchodilators, antihistamines, glucocorticoids, intravenous fluids, vasopressor agents, oxygen, etc. as medically indicated.
 - c. Telephone sponsor or designated representative to report an SAE as per [Section 8.6](#).
 - d. For a NCI-CTCAE Grade 3 or 4 hypersensitivity reaction, discontinue study treatment.
4. Re-treatment following Grade 1 or Grade 2 allergic reactions or cytokine release syndrome:
 - a. Once the PF-06801591 infusion rate has been decreased due to an allergic reaction or cytokine release syndrome, it will remain decreased for all subsequent infusions.

- b. If the patient has a second reaction at the lower infusion rate, the infusion should be stopped and the patient should receive no further PF-06801591.
- c. If the patient experiences a Grade 3 or 4 allergic reaction, cytokine release syndrome, or anaphylaxis at any time, the patient should receive no further PF-06801591.
- d. If there are questions concerning whether an observed reaction is consistent with an allergic reaction, cytokine release syndrome, or anaphylaxis, the medical monitor should be contacted immediately to assist with grading the reaction.

Sampling for PK, pharmacodynamics and ADA should continue as long as the sampling does not interfere with the medical treatment of the patient.

In cases of suspected cytokine release syndrome, a serum sample should be provided for cytokine release assay analysis by the central lab so as long as the sampling does not interfere with the medical treatment of the patient.

Detailed guidance on treatment, dose interruptions and potential retreatment is provided in the DAI.

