5.4.2. SC Administration (Parts 1 and 2)

Qualified and trained investigator site personnel will administer PF-06801591 at a fixed dose of 300 mg to patients by SC injection to the abdomen. A total volume of 6 mL must be administered subcutaneously for a dose of 300 mg of PF-06801591. Ideally, 3 subcutaneous injections of 2 mL should be administered to the abdomen, although, more injections can be done as needed, in order to have a total volume of 6 mL.

Study drug should be administered to two or more different quadrants of the abdomen (with preference given to the lower quadrants when possible); 1 or 2 injections per quadrant. The maximum number of injections per patient is 8 injections. Refer to [Appendix 9](#) for details on administration of multiple injections to the abdomen. Study staff should refer to the IP Manual for specific instructions on the handling and administration of study drug.

Similar to intravenous dosing, a cycle is defined as the time from Day 1 dose to the next Day 1 dose. Patients will receive a single dose of PF-06801591 on Day 1 of each cycle. If there are no treatment delays, a cycle will be 28 days (+/- 2 days) for SC administration. Each patient may receive PF-06801591 until disease progression, unacceptable toxicity, withdrawal of consent, patient no longer willing to participate in trial, or study termination.

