5.4.3.1. Rules For Dose Delay/Interruption/Discontinuation

Events including, but not limited to, pneumonitis, colitis, creatinine, and liver function test (LFT) elevation should be monitored carefully with this class of agents. To facilitate the early recognition and prompt intervention in the event of clinically AEs related to study treatment, management algorithms have been developed for suspected pulmonary, gastrointestinal, liver, endocrine, skin, cardiac, renal, or other immune-related toxicities (See [Appendix 8](#)). For non-irAEs, please refer to the rules for dose delay/interruption/discontinuation below:

- Withhold treatment for: creatinine, AST, ALT, or total bilirubin for drug-related Grade 2 elevations except if they were >ULN at baseline.
- Withhold treatment for any other Grade 3 drug-related AEs.
- Resume treatment when drug-related AE recovers to Grade 0-1 except when creatinine, AST, ALT, or total bilirubin were >ULN at baseline.
- Discontinue treatment for drug-related Grade 3-4 creatinine, AST, ALT, or total bilirubin elevations except if they were >ULN at baseline.
- Discontinue treatment for any other Grade 4 drug-related AEs or laboratory abnormality, except for the following events which do not require discontinuation:
 - Isolated Grade 4 amylase or lipase abnormalities that are not associated with symptoms or clinical manifestations of pancreatitis and decrease to <Grade 4 within 1 week of onset.
 - Isolated Grade 4 electrolyte imbalances/abnormalities that are not associated with clinical sequelae and are corrected with supplementation/appropriate management within 72 hours of their onset.
- Discontinue treatment for persistent Grade 2-3 drug-related AE that do not recover to Grade 0-1 within 12 weeks after last dose except when creatinine, AST, ALT, or total bilirubin were >ULN at baseline.
- Discontinue treatment for any Grade 3-4 drug-related AE that recurs.
- If creatinine >ULN at baseline, withhold treatment for drug-related elevation >1.5 x baseline and resume when ≤ 1.5 x baseline. Discontinue treatment with drug-related elevation >3 x baseline or drug-related elevation that does not recover to ≤ 1.5 x baseline within 12 weeks after last dose.

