5.4.3.2. Infusion Reactions

Following the first administration of some antibody therapeutics, some patients experience fever, headache, nausea, vomiting, or hypotension. These AEs are generally ascribed to lysis of cellular targets, cytokine release, or complement activation.

Clinical management of these events, and the use of pretreatments for subsequent doses, are discussed in [Appendix 7](#).

5.4.3.3. Hypersensitivity Types 1 and 3

Type 1 hypersensitivity or allergic (eg, shortness of breath, urticaria, anaphylaxis, angioedema) reactions are theoretically possible in response to any injected protein. Immune complex mediated Type 3 hypersensitivity reactions are similar to the AEs of Type 1 reactions but are likely to be delayed from the time of administration and may include symptoms such as rash, urticaria, polyarthritis, myalgias, polysynovitis, fever, and, if severe, glomerulonephritis.

All patients should be closely observed while receiving investigational product and monitoring for clinical signs of a systemic reaction will continue thereafter for clinical signs of allergic reactions/hypersensitivity.

Clinical management of these events is discussed in [Appendix 7](#).

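### Appendix 7's permanent stop after a repeat allergic or cytokine-release reaction depends on a reduced infusion rate, so it cannot operate for SC patients; items 2c and 4b, and 5.4.3.1 and Appendix 7, also need reconciling.

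*Protocol*

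**What the plan says.** **SC dosing (Protocol 5.4.2).** The drug is given by injection: "Ideally, 3 subcutaneous injections of 2 mL should be administered to the abdomen." No rate is defined.

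**General rules (Protocol 5.4.3.1).** The scope is set by "For non-irAEs, please refer to the rules for dose delay/interruption/discontinuation below." For Grade 3 events outside the named laboratory tests: "Withhold treatment for any other Grade 3 drug-related AEs." On restarting: "Resume treatment when drug-related AE recovers to Grade 0-1 except when creatinine, AST, ALT, or total bilirubin were >ULN at baseline." On recurrence: "Discontinue treatment for any Grade 3-4 drug-related AE that recurs." The listed exceptions concern amylase or lipase, electrolytes, other isolated laboratory abnormalities and abnormal baseline values. None concerns hypersensitivity.

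**Cross-references (Protocol 5.4.3.2 and 5.4.3.3).** For infusion reactions: "Clinical management of these events, and the use of pretreatments for subsequent doses, are discussed in" Appendix 7. Section 5.4.3.3 does the same for hypersensitivity, and it speaks of reactions to any injected protein, so it is not limited to IV.

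**Specific guidance (Protocol Appendix 7).**
- Item 2 (Grade 2 allergic reaction or cytokine release): stop the infusion, resume at half rate after improvement, stop if it recurs, and premedicate later infusions.
- Item 3d: "For a NCI-CTCAE Grade 3 or 4 hypersensitivity reaction, discontinue study treatment."
- Item 4a: once reduced for such a reaction, the rate stays reduced.
- Item 4b: "If the patient has a second reaction at the lower infusion rate, the infusion should be stopped and the patient should receive no further PF-06801591."
- Item 4c: no further drug after a Grade 3 or 4 allergic reaction, cytokine release syndrome or anaphylaxis, whenever it occurs.
- The closing text refers to the DAI for detail on interruption and retreatment.

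**The concern.** The route used for most of the study does not have the condition on which the repeat-reaction stop depends. Section 5.4.3.3 sends SC hypersensitivity reactions to Appendix 7, but the Grade 1-2 steps there are written for infusion: stop the infusion, halve the rate, keep the lower rate, and stop for good at a second reaction at that rate. Other parts of the protocol were adapted for SC dosing, such as ECG timing (7.1.5), the injection-site assessment (7.1.6) and Appendix 9. These steps were not.

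Sites therefore have to decide for themselves what follows a second Grade 2 reaction to an injection, and an investigator treating a first Grade 3 allergic reaction finds two differently worded instructions. Dose-finding rules give no second line of protection, because Protocol 3.1.5 and SAP Appendix 9.1 exclude Grade 3 or higher infusion and allergic reactions from the DLT definition. The patient-level stop rules carry the weight, so they need to be readable and consistent.

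**Working it through.** No stated figure needs reproducing. The check sets the passages side by side, with one piece of arithmetic.

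**1. Can item 4b be met by an SC patient?** It needs two things: a rate already reduced because of a reaction, and a second reaction at that reduced rate. Section 5.4.2 defines a volume and a number of injections, but no rate. The first condition cannot occur, so neither can the second.

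**2. Does another rule give an automatic permanent stop for repeat Grade 1-2 reactions that resolve?**

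| Rule | Reaches a repeat Grade 1-2 reaction in an SC patient? |
|---|---|
| Appendix 7, items 3d and 4c | No: Grade 3-4 only |
| 5.4.3.1, recurrence | No: Grade 3-4 only |
| 5.4.3.1, persistence | Only a Grade 2-3 event not recovered to Grade 0-1 within 12 weeks of the last dose |
| 5.4.3.1, investigator's judgement of substantial risk | Possible, but discretionary |
| 5.4.5, intolerable Grade 2 toxicity | Interruption or delay, not a permanent stop |

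None of these replaces 4b for acute reactions that resolve.

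**3. How many patients are outside 4b?** Inputs are Protocol 3.1 (Part 2 about 100, all SC; total about 140) and 3.1.1 (Part 1 SC cohort up to about 15).

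- SC patients = 100 + 15 = 115
- Share = 115 / 140 = 0.82, or about 82%

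This includes every Part 2 patient.

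**4. Items 2c and 4b.** Take an IV patient with a Grade 2 reaction, resumed at 50% of the rate, in whom it recurs. Item 2c says stop the infusion, then goes on to premedication for subsequent infusions. Item 4b says a second reaction at the lower rate ends treatment. On the plain sequence of 2c, the same patient both has later infusions and has none.

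**5. A first drug-related Grade 3 allergic reaction that is not an irAE.**

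| | 5.4.3.1 | Appendix 7 |
|---|---|---|
| Immediate step | Withhold | Stop the infusion |
| After recovery to Grade 0-1 | Resume | No further drug (3d, 4c) |
| If Grade 4 | Discontinue (the exceptions are laboratory findings) | No further drug |
| If Grade 3-4 recurs | Discontinue | Already stopped |

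The texts part only in the second row: a first Grade 3 event that recovers.

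**The case against.** The strongest reply is that 5.4.3.1 is the general rule, followed within 5.4.3 by two named subsections that send infusion and hypersensitivity reactions to a specific appendix. A sensible reader would let the specific text prevail. This has force, and it reduces the Grade 3 point to a missing precedence statement. It does not remove it. The subsections refer only clinical management to an appendix titled as recommendations, whose opening on hypersensitivity says that infusions may be stopped. Section 5.4.3.1 is titled as rules for discontinuation and covers non-irAEs without excepting these reactions.

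Items 2c and 4b could also be harmonised by reading the premedication sentence in 2c as applying only to patients whose resumed infusion went well, or 4b as applying only at later infusions. Either is possible, but neither is written.

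On SC dosing, the DAI may cover retreatment. It is not among the documents, so this cannot be checked. A permanent stop that the protocol spells out for one route should still be readable in the protocol for the other.

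Several stronger readings are tempting and are not supported:
- **That SC patients have no stop rule.** Item 4c, the 5.4.3.1 recurrence rule and the investigator-judgement rule do not depend on a rate. Pretreatment in Appendix 7 is likewise tied to each administration, not to an infusion rate.
- **That Appendix 7 ends treatment after any severe infusion reaction.** Its permanent Grade 3-4 stop names allergic or hypersensitivity reactions, cytokine release syndrome and anaphylaxis. Its paragraph on chills, fever or hypotension interrupts and restarts at half rate.
- **That 5.4.3.1 resumes everyone who recovers.** It discontinues recurrent Grade 3-4 events, events slow to recover, and events the investigator judges a substantial risk. Section 5.4.5 adds conditions for resuming after 4 weeks of interruption.
- **That IV-SC comparisons are compromised.** No such comparison is planned, the SAP (5.1) has no hypotheses, and Protocol 3.1.4 keeps SC data out of the IV MTD.

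**Conclusion.** The concern holds in three limited parts.

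1. As written, item 4b cannot operate for SC injection. The gap is the automatic permanent stop after repeat Grade 1-2 allergic or cytokine-release reactions. It covers all of Part 2 and the Part 1 SC cohort, up to about 115 of about 140 planned patients (82%). That figure is the population outside the rule. The documents available give no rate of repeat Grade 1-2 reactions, so the number who would actually be affected cannot be estimated and may be small.
2. Items 2c and 4b conflict on their plain sequence for an IV patient whose reaction recurs at the halved rate.
3. Section 5.4.3.1 and Appendix 7 differ for a first, recovered, drug-related Grade 3 allergic or hypersensitivity reaction, with cross-references but no statement of which governs.

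The consequence is for patient safety and consistent conduct across sites, not for dose finding or any planned analysis. The conclusion rests on planned enrolment and on the DAI not being available; if the DAI sets out SC retreatment, part 1 becomes a matter of carrying that text into the protocol. Which clinical rule is right is not judged here.

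**What to change.** Reconcile the passages by protocol wording:

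- In 5.4.3.1, state which section governs allergic, cytokine-release and infusion reactions, and treat each of the three explicitly, since Appendix 7 handles plain infusion reactions separately.
- In Appendix 7, reconcile items 2c and 4b so that one outcome follows a recurrence at the reduced rate.
- Restate the Appendix 7 re-treatment and stop steps in terms that can operate for SC injection, and check them against the DAI so that the two documents agree.

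The content of each rule is for the sponsor's medical team. The cost is amendment wording and a matching check of the DAI, with no added procedures, visits or patients and no change to the analysis.

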Appendix 8. Management of Immune-related Adverse Events (irAEs)

Gastrointestinal irAEs		
Severity of Diarrhea/Colitis (NCI-CTCAE v4)	Initial Management	Follow-up Management

Grade 1 Diarrhea: <4 stools/day over Baseline Colitis: asymptomatic
	
-Continue study treatment. -Symptomatic treatment (eg, loperamide).
	
-Close monitoring for worsening symptoms. -Educate patient to report worsening immediately. -If worsens: Treat as Grade 2, 3 or 4.

Grade 2 Diarrhea: 4 to 6 stools per day over Baseline; IV fluids indicated <24 hours; not interfering with ADL Colitis: abdominal pain; blood in stool
	
-Withhold study treatment. -Symptomatic treatment.
	
-If improves to Grade ≤1: Resume study treatment. -If persists >5-7 days or recurs: Treat as Grade 3 or 4.

Grade 3 to 4 Diarrhea (Grade 3): ≥7 stools per day over Baseline; incontinence; IV fluids ≥24 h; interfering with ADL Colitis (Grade 3): severe abdominal pain, medical intervention indicated, peritoneal signs Grade 4: life-threatening, perforation
	
-Withhold for Grade 3. -Permanently discontinue study treatment for Grade 4 or recurrent Grade 3. -1.0 to 2.0 mg/kg/day prednisone IV or equivalent. -Add prophylactic antibiotics for opportunistic infections. -Consider lower endoscopy.
	
-If improves: -Continue steroids until Grade ≤1, then taper over at least 1 month; resume study treatment following steroids taper (for initial Grade 3). -If worsens, persists >3 to 5 days, or recurs after improvement: -Add infliximab 5mg/kg (if no contraindication). -Note: infliximab should not be used in cases of perforation or sepsis.

Dermatological irAEs		
Grade of Rash (NCI-CTCAE v4)	Initial Management	Follow-up Management

Grade 1 to 2 Covering \leq30% body surface area
	
 -Continue study treatment. -Symptomatic therapy (for example, antihistamines, topical steroids). 	
 -If persists $>$1 to 2 weeks or recurs: -Withhold study treatment. -Consider skin biopsy. -Consider 0.5-1.0 mg/kg/day prednisone or equivalent. Once improving, taper steroids over at least 1 month, consider prophylactic antibiotics for opportunistic infections, and resume study treatment following steroids taper. -If worsens: Treat as Grade 3 to 4.

Grade 3 to 4 Grade 3: Covering $>$30% body surface area; Grade 4: Life threatening consequences
	
 -Withhold study treatment for Grade 3. -Permanently discontinue for Grade 4 or recurrent Grade 3. -Consider skin biopsy. -Dermatology consult. -1.0 to 2.0 mg/kg/day prednisone or equivalent. -Add prophylactic antibiotics for opportunistic infections. 	
 -If improves to Grade \leq1: -Taper steroids over at least 1 month; resume study treatment following steroids taper (for initial Grade 3).

Pulmonary irAEs		
Grade of Pneumonitis (NCI-CTCAE v4)	Initial Management	Follow-up Management
Grade 1 Radiographic changes only	-Consider withholding study treatment. -Monitor for symptoms every 2 to 3 days. -Consider Pulmonary and Infectious Disease consults.	-Re-assess at least every 3 weeks. -If worsens: Treat as Grade 2 or Grade 3 to 4.
Grade 2 Mild to moderate new symptoms	-Withhold study treatment. -Pulmonary and Infectious Disease consults. -Monitor symptoms daily; consider hospitalization. -1.0 to 2.0 mg/kg/day prednisone or equivalent. -Add prophylactic antibiotics for opportunistic infections. -Consider bronchoscopy, lung biopsy.	-Re-assess every 1 to 3 days If improves: -When symptoms return to Grade ≤ 1 , taper steroids over at least 1 month, and then resume study treatment following steroids taper. -If not improving after 2 weeks or worsening: Treat as Grade 3 to 4.
Grade 3 to 4 Grade 3: Severe new symptoms; New/worsening hypoxia; Grade 4: Life-threatening	-Permanently discontinue study treatment. -Hospitalize. -Pulmonary and Infectious Disease consults. -1.0 to 2.0 mg/kg/day prednisone or equivalent. -Add prophylactic antibiotics for opportunistic infections. -Consider bronchoscopy, lung biopsy.	-If improves to Grade ≤ 1 : -Taper steroids over at least 1 month. -If not improving after 48 hours or worsening: Add additional immunosuppression (for example, infliximab, cyclophosphamide, IV immunoglobulin, or mycophenolate mofetil).

Hepatic irAEs		
Grade of Liver Test Elevation (NCI-CTCAE v4)	Initial Management	Follow-up Management
Grade 1 Grade 1 AST or ALT > ULN to 3.0 x ULN and/or Total bilirubin > ULN to 1.5 x ULN	-Continue study treatment.	-Continue liver function monitoring. -If worsens: Treat as Grade 2 or 3 - 4.
Grade 2 AST or ALT >3.0 to ≤5 x ULN and/or total bilirubin >1.5 to ≤3 x ULN	-Withhold study treatment. -Increase frequency of monitoring to every 3 days.	-If returns to Grade ≤1: -Resume routine monitoring; resume study treatment. -If elevation persists > 5 to 7 days or worsens: -Treat as Grade 3 to 4.
Grade 3 to 4 AST or ALT >5 x ULN and/or total bilirubin >3 x ULN	-Permanently discontinue study treatment. -Increase frequency of monitoring to every 1 to 2 days. -1.0 to 2.0 mg/kg/day prednisone or equivalent. -Add prophylactic antibiotics for opportunistic infections. -Consult gastroenterologist/hepatologist. -Consider obtaining MRI/CT scan of liver and liver biopsy if clinically warranted.	-If returns to Grade ≤1: -Taper steroids over at least 1 month. -If does not improve in >3 to 5 days, worsens or rebounds: -Add mycophenolate mofetil 1 gram (g) twice daily. -If no response within an additional 3 to 5 days, consider other immunosuppressants per local guidelines.

Renal irAEs		
Grade of Creatinine Increased (NCI-CTCAE v4)	Initial Management	Follow-up Management
Grade 1 Creatinine increased > ULN to 1.5 x ULN	-Continue study treatment.	-Continue renal function monitoring. -If worsens: Treat as Grade 2 to 3 or 4.
Grade 2 to 3 Creatinine increased >1.5 and ≤6 x ULN	-Withhold study treatment. -Increase frequency of monitoring to every 3 days. -1.0 to 2.0 mg/kg/day prednisone or equivalent. -Add prophylactic antibiotics for opportunistic infections. -Consider renal biopsy.	-If returns to Grade ≤1: -Taper steroids over at least 1 month, and resume study treatment following steroids taper. -If worsens: -Treat as Grade 4.
Grade 4 Creatinine increased >6 x ULN	-Permanently discontinue study treatment. -Monitor creatinine daily. -1.0 to 2.0 mg/kg/day prednisone or equivalent. -Add prophylactic antibiotics for opportunistic infections Consider renal biopsy. -Nephrology consult.	-If returns to Grade ≤1: Taper steroids over at least 1 month.

Cardiac irAEs		
Myocarditis	Initial Management	Follow-up Management
New onset of cardiac signs or symptoms and / or new laboratory cardiac biomarker elevations (eg, troponin, CK-MB, BNP) or cardiac imaging abnormalities suggestive of myocarditis.	
 -Withhold study treatment. -Hospitalize. -In the presence of life threatening cardiac decompensation, consider transfer to a facility experienced in advanced heart failure and arrhythmia management. -Consult cardiologist to establish etiology and rule-out immune-mediated myocarditis. -Guideline based supportive treatment as per cardiology consult.* -Consider myocardial biopsy if recommended per cardiology consult. 	
 -If symptoms improve and immune-mediated etiology is ruled out, re-start study treatment. -If symptoms do not improve/worsen, viral myocarditis is excluded, and immune-mediated etiology is suspected or confirmed following cardiology consult, manage as immune-mediated myocarditis.
Immune-mediated myocarditis	
 -Permanently discontinue study treatment. -Guideline based supportive treatment as appropriate as per cardiology consult.* 1.0 to 2.0 mg/kg/day prednisone or equivalent. -Add prophylactic antibiotics for opportunistic infections. 	
 -Once improving, taper steroids over at least 1 month. If no improvement or worsening, consider additional immunosuppressants (eg, azathioprine, cyclosporine A).

*Local guidelines, or eg. ESC or AHA guidelines ESC guidelines website: https://www.escardio.org/Guidelines/Clinical-Practice-Guidelines AHA guidelines website: http://professional.heart.org/professional/GuidelinesStatements/searchresults.jsp?q=&y=&t=1001
		

[figure not shown]
Endocrine irAEs		
Endocrine Disorder	Initial Management	Follow-up Management
Grade 1 or Grade 2 endocrinopathies (hypothyroidism, hyperthyroidism, adrenal insufficiency, type I diabetes mellitus)	
 -Continue study treatment. -Endocrinology consult if needed. -Start thyroid hormone replacement therapy (for hypothyroidism), anti-thyroid treatment (for hyperthyroidism), corticosteroids (for adrenal insufficiency) or insulin (for Type I diabetes mellitus) as appropriate. -Rule-out secondary endocrinopathies (ie, hypopituitarism / hypophysitis). 	
 -Continue hormone replacement/suppression and monitoring of endocrine function as appropriate.
Grade 3 or Grade 4 endocrinopathies (hypothyroidism, hyperthyroidism, adrenal insufficiency, type I diabetes mellitus)	
 -Withhold study treatment. -Consider hospitalization. -Endocrinology consult. -Start thyroid hormone replacement therapy (for hypothyroidism), anti-thyroid treatment (for hyperthyroidism), corticosteroids (for adrenal insufficiency) or insulin (for type I diabetes mellitus) as appropriate. -Rule-out secondary endocrinopathies (ie, hypopituitarism / hypophysitis). 	
 -Resume study treatment once symptoms and/or laboratory tests improve to Grade ≤ 1 (with or without hormone replacement/suppression). -Continue hormone replacement/suppression and monitoring of endocrine function as appropriate.
Hypopituitarism/ Hypophysitis (secondary endocrinopathies)	
 -If secondary thyroid and/or adrenal insufficiency is confirmed (ie, subnormal serum FT4 with inappropriately low TSH and/or low serum cortisol with inappropriately low ACTH) : 
 -Refer to endocrinologist for dynamic testing as indicated and measurement of other hormones (FSH, LH, GH/IGF-1, PRL, testosterone in men, estrogens in women). -Hormone replacement/suppressive therapy as appropriate. -Perform pituitary MRI and visual field examination as indicated. -If hypophysitis is confirmed: 
 -Continue study treatment if mild symptoms with normal MRI. Repeat the MRI in 1 month. 	
 -Resume study treatment once symptoms and hormone tests improve to Grade ≤ 1 (with or without hormone replacement). -In addition, for hypophysitis with abnormal MRI, resume study treatment only once shrinkage of the pituitary gland on MRI/CT scan is documented. -Continue hormone replacement/suppression therapy as appropriate.

Endocrine irAEs		
Endocrine Disorder	Initial Management	Follow-up Management
	
-Withhold study treatment if moderate, severe or life-threatening symptoms of hypophysitis and/or abnormal MRI. Consider hospitalization. Initiate corticosteroids (1 to 2 mg/kg/day prednisone or equivalent) followed by corticosteroids taper during at least 1 month.
 
-Add prophylactic antibiotics for opportunistic infections.
	

Other irAEs (not described above)		
Grade of other irAEs (NCI-CTCAE v4)	Initial Management	Follow-up Management
Grade 2 or Grade 3 clinical signs or symptoms suggestive of a potential irAE	-Withhold study treatment pending clinical investigation.	-If irAE is ruled out, manage as appropriate according to the diagnosis and consider re-starting study treatment -If irAE is confirmed, treat as Grade 2 or 3 irAE.
Grade 2 irAE or first occurrence of Grade 3 irAE	-Withhold study treatment. -1.0 to 2.0 mg/kg/day prednisone or equivalent. -Add prophylactic antibiotics for opportunistic infections. -Specialty consult as appropriate.	-If improves to Grade \leq 1: -Taper steroids over at least 1 month and resume study treatment following steroids taper.
Recurrence of same Grade 3 irAEs	-Permanently discontinue study treatment. -1.0 to 2.0 mg/kg/day prednisone or equivalent. -Add prophylactic antibiotics for opportunistic infections. -Specialty consult as appropriate.	-If improves to Grade \leq 1: Taper steroids over at least 1 month.
Grade 4	-Permanently discontinue study treatment. -1.0 to 2.0 mg/kg/day prednisone or equivalent and/or other immunosuppressant as needed -Add prophylactic antibiotics for opportunistic infections. -Specialty consult.	-If improves to Grade \leq 1: Taper steroids over at least 1 month.
Requirement for 10 mg per day or greater prednisone or equivalent for more than 12 weeks for reasons other than hormonal replacement for adrenal insufficiency	- Permanently discontinue study treatment. -Specialty consult.	
Persistent Grade 2 or 3 irAE lasting 12 weeks or longer		

Abbreviations: ACTH=adrenocorticotropic hormone; ADL=activities of daily living; ALT=alanine aminotransferase; AST=aspartate aminotransferase; BNP=B-type natriuretic peptide; CK-MB=creatin kinase MB; CT= computed tomography; FSH=follicle-stimulating hormone; GH=growth hormone; IGF-1=insulin-like growth factor 1; irAE=immune-related adverse event; IV=intravenous; LH=luteinizing hormone; MRI=magnetic resonance imaging; NCI-CTCAE=National Cancer Institute-Common Terminology Criteria for Adverse Events; PRL=prolactin; T4=thyroxine; TSH=thyroid-stimulating hormone; ULN=upper limit of normal.

